3.3.3 Questionnaires

We will assess knowledge about HPV and HPVv and attitudes towards HPVv with a questionnaire administered at Ti (right before the educational session) and at T6. In order to preserve blinding of the control group with respect to HPVv, the survey will be the same for all participants and will include analogous questions about other vaccinations (herpes zoster, pneumococci, and TBE).

The HPVv-specific section of the questionnaire will comprise

- Nine questions on attitudes towards HPVv (4.1–4.9). Of these, 7 questions (4.1–4.3, 4.5–4.8) are Likert-type (levels Disagree/Rather disagree/Neutral/Rather agree/Agree), one is multiple-choice (4.4), and one is single-choice (4.9). Both the single- and multiple-choice question have a free-text option. The sections specific to all other vaccinations will contain the same questions.
- Five single-choice questions on knowledge about HPV (4.10–4.14). Of these, two questions (4.11, 4.12) consist of 7 sub-questions with respectively identical answer options each.

1	TI (/T7 111			T .•	TRA		TT (T 14	
	for eligibility and delivery of the inte	rvention.							
	Table 1. Overview of study timings	. The inclusio	on perio	d refers to	the time fra	ame betweer	1 approach	ing the GP	

Event/Variable	Inclusion period	Ti	T0	Т3	T6	T12
Eligibility determination						
Recruitment						
Randomization						
Baseline characteristics of GPs						
Baseline HPVv count						
Questionnaires						
Delivery of intervention						
Start of HPVv documentation						
Reporting of HPVv documentation						
End of HPVv documentation						

4 Analysis

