4.1.2 Secondary Objectives

- (1) To compare the first-dose HPVv counts at T3 and T12 between the intervention group and the control group.
- (2) To compare the number of overall HPVv counts at T3, T6, and T12 between the intervention group and the control group.
- (3) To compare the change of overall HPVv counts at T3, T6 and T12 with respect to Pb between the intervention group and the control group.
- (4) To compare the change in HPV-related knowledge at T6 with respect to Ti (before delivery of the intervention) between the active intervention group and the control group.
- (5) To compare the change in attitudes towards HPVv at T6 with respect to Ti (before delivery of the intervention) between the active intervention group and the control group.
- (6) To describe demographic characteristics of patients obtaining HPVv (gender and age).
- (7) To describe the following characteristics of administered HPVv: first dose or later vaccination, request of patient or recommendation by GP (or both), and HPVv administered alone or in combination with other vaccines.

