4.2.2 Analysis of Questionnaire Responses

We will provide descriptive summaries of the questionnaire answers to all vaccinations at Ti (before delivery of the intervention) and T6. No stratification into study arm will be implemented. Answers to questionnaire items containing free-text options will be categorized in either one of the provided answer options, if applicable, or as "other answer".

For questionnaire items expressed as Likert-type scales, we will assign integer scores to the responses ranging from 1 for "Disagree" to 5 for "Agree". We will provide a measure of internal consistency by means of Cronbach's alpha. The test-retest reliability will be assessed by calculating Pearson correlation coefficients between each GP's summated scores at Ti and T6, in each study arm separately.

For each GP, we will calculate an HPV knowledge score as the sum of all correct answers to the knowledge-related questions as well as an HPVv attitude score as the sum of all Likert-type answer scores to the attitude-related questions. We will use Wilcoxon signed-rank tests to assess for differences in HPV knowledge and HPVv attitude scores between Ti and T6.

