4.2.4 Analysis of the Secondary Objectives

For the secondary objectives, we will use the following procedures:

- (1) Analogous models as for the primary objective, using the first HPVv dose count at the respective time point and assessing the coefficient estimate of the study arm together with 95% confidence intervals.
- (2) Analogous models as for the primary objective, but using the count of all administered HPVv doses instead of the number of first HPVv doses at the respective time points as the outcome variable. We will base assessment of this objective on the estimated coefficient of the study arm for the respective time points together with 95% confidence intervals.
- (3) We will model this objective with logistic regression. The binary outcome variable will indicate whether the overall count of administered HPVv doses at T6 will have increased with respect to the value indicated for Pb. Model covariates will include GP gender, workload (categorized as for the primary objective), and participation status in the cantonal HPVv program at inclusion.
- (4) To assess this objective, we will use logistic regression on a binary outcome indicating, for each GP, whether their HPV knowledge score will have increased from Ti to T6. The model will include the following covariates: study arm, baseline HPV knowledge score, GP gender, GP workload (categorized as for the primary objective), and participation status in the cantonal HPVv program at inclusion.
- (5) We will assess this objective by a logistic regression model analogous to the model for secondary objective 4. The binary outcome variable will indicate, for each GP, whether their HPVv attitude score will have increased from Ti to T6. Adjustment will occur for the baseline HPVv attitude score instead of the HPV knowledge score.
- (6) Tabulation and assessment of group differences as described in section 4.2.1.
- (7) Tabulation and assessment of group differences as described in section 4.2.1.

For each of the fitted regression models, we will report the results and inferred implications of standard model diagnostics procedures, such as assessment for overdispersion, residual and random effect analyses, influential point analyses, and checks for multicollinearity. Accordingly, we will adapt models as necessary (e.g., by log-transforming continuous variables, by excluding ill-defined variables from the model equations or by considering non-parametric alternatives where deemed appropriate).

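### Secondary objectives 4 and 5: cutting the numeric knowledge and attitude scores to any increase versus none costs precision, and no other planned analysis compares the scores between arms

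*SAP*

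**What the plan says.** SAP section 4.1.2 states objective 4 as "To compare the change in HPV-related knowledge at T6 with respect to Ti", between the two arms. Objective 5 has the same form for attitudes.

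Section 4.2.2 builds two numeric scores per GP: an "HPV knowledge score as the sum of all correct answers to the knowledge-related questions", and an "HPVv attitude score as the sum of all Likert-type answer scores to the attitude-related questions". Likert answers are scored 1 to 5.

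In section 4.2.4, item (4) takes as its outcome, for each GP, "whether their HPV knowledge score will have increased from Ti to T6", and item (5) takes "whether their HPVv attitude score will have increased from Ti to T6". Both are fitted by logistic regression. The covariates in item (4) are "study arm, baseline HPV knowledge score, GP gender, GP workload" and cantonal programme status; item (5) replaces the baseline knowledge score with the baseline attitude score. The SAP gives no reason for the cut, no threshold for a meaningful gain, and no separate rule for unchanged scores or for GPs already at the maximum.

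The numeric scores are otherwise used only in section 4.2.2: Wilcoxon signed-rank tests of Ti against T6, and reliability statistics. The first paragraph of that section, on summaries of the questionnaire answers, says "No stratification into study arm will be implemented".

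**The concern.** The objectives ask how far knowledge and attitudes change in one arm compared with the other. The planned outcome keeps only the sign of each GP's change. A gain of 1 point counts the same as a gain of 10, and no change counts the same as a fall. A GP at the top of the scale at Ti is coded as not increased in either arm, whatever happens later.

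At stake is precision in a small trial. The odds of any increase say little about the size of an educational effect, and an interval for them will be wide. Section 3.1 says that effect sizes will be weighed alongside p-values for secondary outcomes. A mean difference in score serves that purpose better than an odds ratio from this cut.

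**Working it through.** **Stated figures.** The SAP gives no power or effect size for these scores, so there is no figure to reproduce. Section 2.4 is used only for the number of GPs. It states 33 without saying whether that is the total or per arm, so 33 and 66 are both shown.

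**Score ranges.**
- Attitude: seven Likert items (section 3.3.3) scored 1 to 5 give 7 × 1 = 7 to 7 × 5 = 35.
- Knowledge: section 3.3.3 lists five questions and adds: "Of these, two questions (4.11, 4.12) consist of 7 sub-questions with respectively identical answer options each". If each sub-question earns a point, the maximum is 3 + 2 × 7 = 17. If not, it is 5.

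**Information kept by the cut.** Assume roughly normal change scores, with a share p of GPs increasing. The efficiency of the yes/no outcome relative to the numeric one is φ(z)² / [p(1 − p)], where z is the normal quantile of p. The values of p are assumptions. The last column is the power left to an analysis that would have 80% on the numeric score: Φ[(1.960 + 0.842) × √efficiency − 1.960].

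| Share increasing | φ(z) | Efficiency | Loss | Power left from 80% |
|---|---|---|---|---|
| 50% | 0.399 | 0.637 | 36.3% | 61% |
| 60% | 0.386 | 0.622 | 37.8% | 60% |
| 70% | 0.348 | 0.576 | 42.4% | 57% |
| 80% | 0.280 | 0.490 | 51.0% | 50% |

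The 50% row is the best case. There, 33 GPs carry the information of 33 × 0.637 = 21, and 66 that of 42.

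**Check on bounded integer scores.** Scores were simulated as rounded normals cut at the scale limits, with 66 GPs. All settings are assumptions:
- Knowledge: baseline means 10 to 15.5, SD 2.5, correlation 0.5, gains of 0.5 (control) and 2.0 (active).
- Attitude: baseline means 24 to 31, SD 4, correlation 0.6, gains of 0.5 and 2.8.

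ANCOVA on the T6 score was compared with logistic regression on any increase, both adjusted for the Ti score only and without practice clustering. Together with runs at 400 GPs and smaller effects, the loss was 41% to 58%. At 66 GPs, power was 64% to 80% for ANCOVA and 34% to 57% for the logistic model. For knowledge at 66 GPs, the loss rose from about 45% with 0.5% of GPs at the ceiling at Ti, to 47% with 16%, and 58% with 35%. With heavy-tailed (Laplace) errors, at 400 GPs, the loss fell to about 21%.

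**Size of the logistic model.** Arm 1, baseline score 1, gender 1, workload 2 (three levels), programme status 1: six coefficients besides the intercept. With an assumed 60% increasing, the rarer class holds 40%:
- 33 GPs in total: 0.4 × 33 ≈ 13, and 13 / 6 ≈ 2 per coefficient.
- 66 GPs in total: 0.4 × 66 ≈ 26, and 26 / 6 ≈ 4 per coefficient.

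**Whether another analysis fills the gap.** The signed-rank tests compare Ti with T6 within GPs, so they do not compare the arms even if run in each arm. The by-arm correlations in section 4.2.2 measure reliability. The practice-level sensitivity analysis in section 4.2.5 covers only the primary objective.

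**The case against.** The strongest defence has four parts.

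- **Exploratory status.** Section 3.1 makes secondary outcomes exploratory, so the trial's main conclusion is untouched. That is right, and it limits the weight of the point.
- **A legitimate summary.** The objectives speak of change in knowledge and attitudes, not of change in a score. The share improving is one way to express that, and it avoids treating summed Likert items as an interval scale. So the SAP does not contradict itself here. The loss of precision remains, and the SAP gives no reason for accepting it.
- **Baseline adjustment.** Both models include the Ti score, which addresses differing room to improve. It does not change the coding of a GP who cannot rise.
- **Model adaptation.** Section 4.2.4 allows models to be changed after diagnostics, for example by dropping ill-defined variables. This could ease separation. It is discretionary and does not commit to analysing the numeric scores.

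A reader might also draw three stronger conclusions that the document does not support. First, that the Wilcoxon tests pool the arms: the sentence on stratification belongs to the descriptive summaries, the next paragraph computes reliability in each arm separately, and the text on the Wilcoxon tests does not mention arm. Second, that over a third of the information is lost in any event: the SAP gives no score distribution, and the loss was about 21% under heavy tails. Third, that the ceiling is known to distort the result: the share of GPs at the maximum is not given and may be small.

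**Conclusion.** The point holds as an avoidable loss of precision in two exploratory analyses, together with the lack of any between-arm comparison of the numeric scores. Under near-normal change scores the loss is at least 36%, and 42% if 70% of GPs increase. It was larger in the simulated bounded scores and smaller with heavy-tailed errors. The coding of GPs at the maximum follows from the definition, but its practical size is unknown. The figures of 2 to 4 rarer-class GPs per coefficient rest on an assumed 60% increasing and on whether 33 or 66 GPs are enrolled; they point to a risk of unstable estimates or separation. The primary analysis is not affected.

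**What to change.** In section 4.2.4, items (4) and (5), analyse the T6 score by ANCOVA, fitted as a linear mixed model. Include study arm, the Ti score and the covariates already listed (GP gender, workload, programme status). Add a practice random intercept, because section 2.2 randomises practices and these items have no practice term. Report the adjusted mean difference between arms with its 95% confidence interval, and check the residuals. Keep the yes/no outcome as a descriptive summary. In section 4.2.2, present the Ti and T6 score summaries by arm, and state whether sub-questions of 4.11 and 4.12 each count one point.

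The cost is SAP wording only; no new data are needed. There are two small drawbacks: the model assumes approximate normality of a bounded score, and the T6 score still has a ceiling, so ANCOVA lessens that problem without removing it.

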2.4 Sample Size

According to the study protocol (2), a sample size of 33 GPs, each recruiting 30 patients, will achieve a power of 80% at an alpha of 5% to detect a coverage change of +9.5% in the control group and of +14.9% in the active intervention group (according to a similar study (3))

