3.1 Confidence Intervals and *p*-Values

We will report statistical significance as determined in statistical null hypothesis tests by means of p-values. A level of significance of 0.05 will be used throughout the analyses. Accordingly, we will report two-sided 95% confidence intervals of coefficient estimates.

We will use a mixed-effects regression model for assessment of the primary objective and we will base rejection of the null hypothesis (no difference in effect on HPVv counts at T6 between the control and

intervention group related to the study hypothesis (see section 1.2) on statistical significance of a specific fixed effect coefficient estimate (see section 4.2.3).

Secondary outcomes will be assessed in an exploratory manner, and no adjustment for multiplicity will be implemented. We will judge resulting *p*-values with appropriate caution and consider the corresponding effect sizes.

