4.2.3 Analysis of the Primary Objective

To analyze the primary objective, we will model the count of first administered HPVv doses at T6 using mixed-effect Poisson regression. The outcome variable will be the count of first HPVv doses administered by each GP at each of the time points T3 or T6. GP-level random intercepts will account for intra-GP correlation. The following fixed effects will define the grouping variables of the data set:

- Study arm (binary with levels control; active)
- Time point (binary with levels T3; T6)
- Baseline HPVv count (categorical with levels Never; Rarely (1–5 doses); Occasionally (6–10 doses); Regularly (at least 11 doses))
- GP gender (binary with levels male; female)
- GP age in years (continuous)
- GP workload (categorical with levels < 60%; 60–79%; 80–100%; based on the distribution of consultation counts according to workload in Swiss primary care (4))
- GP participation status in the cantonal HPVv program at inclusion (binary with levels yes; no)
- Patient gender (binary with levels male; female).

Each fixed effect other than the study arm will be included in the final model if a corresponding univariate analysis results in a *p*-value ≤ 0.2 .

The Poisson regression model will be assessed for overdispersion based on an asymptotic chi-squared test for the sum of squared residuals (5, 6). If the null hypothesis of no overdispersion is rejected at the 0.05 level, we will replace the Poisson model by a negative binomial model with the same fixed- and random-effect structure. A quasi-Poisson model will be considered as an alternative in case of an observed linear variance-to-mean relationship (7).

Rejection of the null hypothesis related to the primary objective (the effect associated with the study arm is equal to zero) will be based on the parameter estimate of study arm and its 95% confidence interval in the final model.

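### Secondary objectives 4 and 5 fit six-slope logistic models to about 33 GPs with no small-sample estimator: a real arm effect would tend to be overstated, and some fits would have no finite estimate

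*SAP*

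**What the plan says.** SAP section 4.2.4, item (4), specifies "logistic regression on a binary outcome indicating, for each GP, whether their HPV knowledge score will have increased from Ti to T6". It continues: "The model will include the following covariates: study arm, baseline HPV knowledge score, GP gender, GP workload", followed by participation in the cantonal programme at inclusion. Item (5) repeats the model for the attitude score, with baseline attitude in place of baseline knowledge. The univariate screen in section 4.2.3 is not mentioned for these models, so all covariates go in. That section gives workload three levels.

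Section 2.4 plans "a sample size of 33 GPs, each recruiting 30 patients" and does not say whether 33 is the total or per arm. Section 4.3 makes the main analysis complete-case and anticipates low drop-out.

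Section 3.1 calls the secondary outcomes exploratory. It says their p-values will be read "with appropriate caution and consider the corresponding effect sizes", and it commits to confidence intervals: "we will report two-sided 95% confidence intervals of coefficient estimates". The closing paragraph of section 4.2.4 promises diagnostics for every regression model and allows models to be adapted afterwards, for instance by removing ill-defined variables or turning to non-parametric methods. No section names a penalised or exact method.

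**The concern.** Logistic regression without further qualification is fitted by maximum likelihood. With few observations per coefficient, that estimator has two known faults. Estimates of non-null effects are biased away from zero. Also, the covariates may split improvers from non-improvers perfectly (separation), and then no finite estimate exists.

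What is at stake is the reported size of the intervention's effect on GP knowledge and attitudes. If the intervention works, the published odds ratio would tend to look larger than the truth. If a fit separates, the analyst must improvise after seeing the data.

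**Working it through.** **Inputs from the SAP.** 33 GPs, 30 patients each (2.4); one binary outcome per GP (4.2.4); three workload levels (4.2.3); complete cases (4.3).

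**Step 1: what does 33 mean?** Section 2.4 sizes the trial "to detect a coverage change of +9.5% in the control group and of +14.9% in the active intervention group" with 80% power at 5% alpha. Per arm, n = [z_α·√(2p̄q̄) + z_β·√(p₁q₁ + p₂q₂)]² / d², with p₁ = 0.095, p₂ = 0.149, p̄ = 0.122, d = 0.054.

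- One-sided: (1.645 × 0.4629 + 0.842 × 0.4613)² / 0.054² ≈ 454 per arm. The continuity correction raises this to 490, so 980 / 30 = 32.7, i.e. 33 GPs in total without clustering.
- Two-sided: 576 per arm, so 1,152 / 30 = 38.4 GPs in total. With an assumed ICC of 0.025 the design effect is 1 + 29 × 0.025 = 1.725, and 576 × 1.725 / 30 = 33.1 GPs per arm.

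The plain reading is a total, and the figure can be reproduced that way. The SAP gives no ICC, so the per-arm reading stays possible and is carried below as 66 GPs.

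**Step 2: slopes.** Arm 1 + baseline score 1 + gender 1 + workload 2 + programme status 1 = 6, plus an intercept.

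**Step 3: GPs per slope in the smaller outcome group** (33 GPs; improvement rates are assumptions).

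- 50% improving: 16 / 6 = 2.7
- 60% improving: 33 × 0.40 / 6 = 2.2
- 75% improving: 33 × 0.25 / 6 = 1.4

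**Step 4: simulation of the six-slope model.** Assumptions: 1:1 allocation, gender 50/50, workload 20/30/50%, 70% programme participation, standardised baseline score with slope −0.5, no true effect of the other covariates, no practice clustering; 1,500 data sets per row. Separation was detected by linear programming. Maximum-likelihood (ML) errors are over finite fits only. Firth, which maximises ℓ(β) + ½ log|I(β)|, was also fitted to separated sets and converged in at least 97% of sets at every sample size.

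| GPs | True OR | Control rate | No finite ML fit | ML mean error, log OR | ML median error | Firth mean error |
|---|---|---|---|---|---|---|
| 33 | 3 | 0.3 | 11.3% | +37% | +26% | +4% |
| 33 | 3 | 0.5 | 13.9% | +38% | +25% | +5% |
| 33 | 3 | 0.7 | 44.5% | +32% | +21% | +3% |
| 33 | 2 | 0.4 | 9.1% | +45% | +30% | +6% |
| 33 | 2 | 0.5 | 9.9% | +48% | +38% | +8% |
| 28 | 3 | 0.5 | 23.5% | +56% | +35% | +6% |
| 66 | 3 | 0.5 | 0.8% | +17% | +13% | +2% |
| 66 | 3 | 0.7 | 7.0% | +16% | +11% | −1% |

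**Step 5: fixing the overall improvement rate instead** (33 GPs, true log OR 1.10, score slope −0.8; 2,000 data sets each).

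- 60% improving: ML mean 1.547, i.e. 1.547 / 1.099 − 1 = +41%. On the odds-ratio scale exp(1.547) = 4.7 against 3.0. Separated 12.2%; Firth mean 1.137 (+3%).
- 75% improving: ML mean 1.595 (+45%). Separated 29.5%; Firth mean 1.166 (+6%).
- Median fitted odds ratios are 3.9 and 4.1, i.e. +24% and +28% on the log scale.

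A smaller repeat (600 data sets each) gave +42% with 11% separated and +30% with 33% separated. A further run over odds ratios 2 to 3 and 60 to 75% improving gave mean inflation of about 34 to 52%, with 12 to 41% of fits not finite and Firth within about +11%.

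**Step 6: limits.** Over a wider grid at 33 GPs (odds ratio 2 to 4, score slope 0 to −1.5), mean inflation ran from 17 to 97% and the median from 17 to 46%. At a true odds ratio of 1 there was no systematic shift, Wald tests rejected in 2 to 6% of sets, and 5 to 24% of sets separated.

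**The case against.** **The SAP does not fix any particular inflation.** This stands. A reader might infer that the arm effect will be inflated by about 40%. The document gives no improvement rate, odds ratio or covariate mix. The mean depends on all three, is taken over finite fits, and exceeds the median. Only a conditional range can be defended.

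**33 may be per arm.** This also stands. At 66 GPs the bias is modest and separation rare, although the direction is unchanged.

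**The analyses are exploratory, and section 3.1 does not replace p-values by effect sizes.** Correct: it uses both. That limits the seriousness of the point. It does not remove it, because effect size is one of the two things to be read, and it is what maximum likelihood distorts here.

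**The adaptation clause in section 4.2.4 already covers this.** Only in part. Small-sample bias leaves no trace in residual, influence or multicollinearity checks, so those diagnostics would not prompt a change. For separation, removing a variable makes the adjustment set depend on the data. If study arm itself separates, the clause yields no arm estimate.

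**Item (3) and the covariate list.** A reader might extend the point to item (3), or conclude that gender and workload must go. Neither follows. Item (3) lists four slopes and was not simulated. Replacing gender and workload there (three coefficients) by the four-level baseline category (also three) saves nothing. In items (4) and (5), dropping covariates changes the conditional odds ratio being estimated and is unnecessary once a penalised estimator is used.

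**Conclusion.** The point holds for items (4) and (5) as a cheap improvement to exploratory analyses. With 33 GPs in total, a true arm odds ratio of 2 to 3 and 60 to 75% of GPs improving, default maximum likelihood overstates the arm log odds ratio by roughly 30 to 50% on average among finite fits (median about 20 to 45%). About 10 to 45% of fits have no finite estimate. With 66 GPs the inflation is about 10 to 25% and separation is rare.

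The conclusion rests on the assumed improvement rates, odds ratios and covariate mix, and on taking unqualified logistic regression to mean maximum likelihood. It should not be read as a claim of excess false positives: a null effect is not systematically shifted. The rejection rates above ignore practice clustering, so they do not establish that type I error is sound either.

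**What to change.** In section 4.2.4, items (4) and (5), keep the listed covariates and name the estimator: Firth-penalised logistic regression, with penalised profile-likelihood 95% confidence intervals for the study-arm odds ratio. State that it is used whether or not separation occurs, so that the choice does not depend on the data.

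The cost is a sentence of SAP text and a different R function. The downside is that estimates are shrunk slightly and fewer results may be nominally significant.
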